10.3.4 Reporting of SAEs

SAE reporting to UCB via paper data collection tool

- Initial notification via telephone does not replace the need for the investigator to complete and sign the SAE data collection tool within the designated reporting timeframes.
- Contacts for SAE reporting can be found in [SERIOUS ADVERSE EVENT REPORTING](#).

This document cannot be used to support any marketing authorization application and any extensions or variations thereof.
PUBLIC COPY

10.4 Appendix 4: Contraceptive guidance and collection of pregnancy information

Definitions

Woman of childbearing potential (WOCBP)

A woman is considered fertile following menarche and until becoming postmenopausal unless permanently sterile (see below).

Women in the following categories **are not considered WOCBP**:

1. Premenarchal
2. Premenopausal female with 1 of the following:
 - Documented hysterectomy
 - Documented bilateral salpingectomy
 - Documented bilateral oophorectomy
3. Postmenopausal female
 - A postmenopausal state is defined as no menses for 12 months without an alternative medical cause. A high follicle stimulating hormone (FSH) level in the postmenopausal range may be used to confirm a postmenopausal state in women not using hormonal contraception or HRT. However, in the absence of 12 months of amenorrhea, a single FSH measurement is insufficient.
 - Females on HRT and whose menopausal status is in doubt will be required to use one of the nonestrogen hormonal highly effective contraception methods if they wish to continue their HRT during the study. Otherwise, they must discontinue HRT to allow confirmation of postmenopausal status before study enrollment.

Contraception guidance

Male participants

Male participants with female partners of childbearing potential are eligible to participate if they agree to ONE of the following during the protocol-defined time frame in Section 5.1:

- Are abstinent from penile-vaginal intercourse as their usual and preferred lifestyle (abstinent on a long-term and persistent basis) and agree to remain abstinent.
- Agree to use a male condom plus partner use of a contraceptive method with a failure rate of <1% per year as described in the table below when having penile-vaginal intercourse with a WOCBP who is not currently pregnant.

In addition, male participants must refrain from donating sperm for the duration of the study and for 3 months after the final dose of study intervention.

Male participants with a pregnant or breastfeeding (including pumping breastmilk to feed a child) partner must agree to remain abstinent from penile-vaginal intercourse or use a male

condom during each episode of penile penetration during the protocol-defined time frame and for 1 week after the final dose of study medication.

Female participants

Female participants of childbearing potential are eligible to participate if they agree to use a highly effective method of contraception consistently and correctly as described in the [Table 10–2](#) below.

Table 10–2: Highly effective contraceptive methods^a

Highly effective contraceptive methods that are user dependent^{b,c,d}
Failure rate of <1% per year when used consistently and correctly.
Combined (estrogen and progestogen containing) hormonal contraception associated with inhibition of ovulation ^{c,d} 
• Oral• Intravaginal• Transdermal
Progestogen only hormonal contraception associated with inhibition of ovulation 
• Oral• Injectable
Highly effective methods that are user independent^{c,d}

• Implantable progestogen only hormonal contraception associated with inhibition of ovulation• IUD• IUS• Bilateral tubal occlusion
Vasectomized partner
A vasectomized partner is a highly effective contraception method provided that the partner is the sole male sexual partner of the WOCBP and the absence of sperm has been confirmed. If not, an additional highly effective method of contraception should be used.
Sexual abstinence
Sexual abstinence is considered a highly effective method only if defined as refraining from heterosexual intercourse during the entire period of risk associated with the study intervention. The reliability of sexual abstinence needs to be evaluated in relation to the duration of the study and the preferred and usual lifestyle of the participant.

IUD=intrauterine device; IUS=intrauterine hormone-releasing system; WOCBP=woman of childbearing potential

^a In case of newly started contraception pills/IUDs, the principal investigator should consider the correct timing of starting/applying such methods in relation to the menstrual cycle and the manufacturing instruction as to when these newly started methods would become effective.

^b Typical use failure rates may differ from those when used consistently and correctly. Use should be consistent with local regulations regarding the use of contraceptive methods for participants participating in clinical studies.

^c If locally required, in accordance with Clinical Trial Facilitation Group guidelines, acceptable contraceptive methods are limited to those which inhibit ovulation as the primary mode of action.

^d Hormonal contraception may be susceptible to interaction with the study intervention, which may reduce the efficacy of the contraceptive method. In this case, male condoms must be used in addition to hormonal contraception during the Treatment Period and for at least 1 week after the final dose of study intervention.

Pregnancy testing

- WOCBP should only be included after a confirmed menstrual period and a negative highly sensitive serum pregnancy test at the Screening Visit.
- Additional pregnancy testing should be performed on Day -1 and at the SFU Visit after the final dose of study intervention and as required locally.
- Pregnancy testing will be performed whenever a menstrual cycle is missed or when pregnancy is otherwise suspected.
- Pregnancy testing, with a sensitivity of 25 mIU/mL will be performed.

Male participants with partners who become pregnant

- The investigator will attempt to collect pregnancy information on any male participant's female partner who becomes pregnant while the male participant is in this study. This applies only to male participants who receive study intervention. If the study participant is later found to be on placebo, then pregnancy data collection can stop.
- After obtaining the necessary signed informed consent from the pregnant female partner directly, the investigator will record pregnancy information on the appropriate form and submit it to the sponsor within 1 working day of learning of the partner's pregnancy. The female partner will also be followed to determine the outcome of the pregnancy. Information on the status of the mother and child will be forwarded to the sponsor. Generally, the follow up will be at least 12 months after the delivery date. Any termination of the pregnancy will be reported regardless of fetal status (presence or absence of anomalies) or indication for the procedure.

Female participants who become pregnant

- Any female participant who becomes pregnant while participating in the study will discontinue study intervention.
- The investigator will collect pregnancy information on any female participant who becomes pregnant while participating in this study. Upon notification of a pregnancy, the investigator must immediately (within 24 hours) notify UCB's Patient Safety department by entering all pregnancy information on the appropriate pregnancy paper forms provided by UCB. The participant will be followed to determine the outcome of the pregnancy. The investigator will collect follow-up information on the participant and the neonate, and the information will be forwarded to the sponsor via an update to ClinBase. Generally, the follow up will be at least 12 months after the delivery date. Any termination of pregnancy will be reported, regardless of fetal status (presence or absence of anomalies) or indication for the procedure.
- While pregnancy itself is not considered to be an AE, any pregnancy will need to be reported to UCB Patient Safety. In some circumstances a pregnancy-related AE or outcome should be considered as an SAE: miscarriage, elective abortion when medically indicated (eg, when pregnancy is endangering life or health of mother or when fetus will be born with severe abnormalities), unintended pregnancy after hormonal contraceptive failure (if the hormonal contraceptive was correctly used), ectopic pregnancy, fetal demise, or any congenital anomaly/birth defect of the baby. Any post-study pregnancy-related SAE in either the mother or the neonate considered reasonably related to the study intervention by the investigator will

be reported to the sponsor as described in Section 8.4.5. While the investigator is not obligated to actively seek this information in former study participants, he or she may learn of an SAE through spontaneous reporting.

PUBLIC COPY
This document cannot be used to support any marketing authorization
application and any extensions or variations thereof.

10.5 Appendix 5: Genetics

Use and analysis of deoxyribonucleic acid (DNA)

- Normal inter-individual and inter-ethnic genetic variation may impact a participant's response to study medication due to how it may affect the way the body handles the drug (ie, drug absorption, distribution, metabolism, and excretion). In addition, genetic differences may also play a role in determining response to the drug, where response is defined broadly to include safety and tolerability.
- Deoxyribonucleic acid samples will only be used for research related to exposure and response to minzasolmin. They may also be used to develop tests/assays including diagnostic tests related to minzasolmin. Genetic research may consist of the analysis of 1 or more candidate genes or the analysis of genetic markers throughout the genome.
- The samples may be analyzed as part of a multi-study assessment of genetic factors involved in the response to minzasolmin or study medications of this class to understand study disease or related conditions.
- The results of genetic analyses may be reported in the Clinical Study Report or in a separate study summary.
- The sponsor will store the DNA samples in a secure storage space with adequate measures to protect confidentiality.
- The samples will be retained while research on minzasolmin continues but no longer than 20 years or other period as per local requirements.

10.6 Appendix 6: Liver safety – Suggested actions and follow-up assessments

Participants with PDILI must be assessed to determine if study intervention must be discontinued. In addition, all concomitant medications and herbal supplements that are not medically necessary should also be discontinued.

Investigators should attempt to obtain information on study participants in the case of study intervention discontinuation to complete the final evaluation.

Study participants with PDILI should not be withdrawn from the study until investigation and monitoring are complete. All results of these evaluations and observations, as well as the reason(s) for study intervention discontinuation and/or participant withdrawal (if applicable), must be recorded in the source documents. ClinBase must document the primary reason for discontinuation of study intervention.

A specific monitoring plan must be agreed between the study physician and the investigator for study participants who have ALT >5 ULN. The monitoring plan should include any necessary follow-up assessments (until resolution of the abnormal laboratory values).

Phase 1 liver chemistry stopping criteria are designed to assure participant safety and to evaluate liver event etiology (see Section 7.1.1 and Table 10-3).

Table 10-3: Phase 1 liver chemistry stopping criteria and follow up assessments table

Liver Chemistry Stopping Criteria	
Required Actions and Follow up Assessments	
Actions	Follow up Assessments

ALT-absolute
 
ALT \geq3xULN If ALT \geq3xULN AND bilirubin \geq2xULN ($>35\%$ direct bilirubin) or INR >1.5, report as a SAE^{ab} See additional actions and follow-up assessments below
	
• Immediately discontinue study intervention• Report the event to the sponsor within 24 hours• Complete ClinBase, and complete an SAE data collection tool if the event also met the criteria for an SAE^b• Perform liver function follow-up assessments• Monitor the participant until liver function test abnormalities resolve, stabilize, or return to baseline (see MONITORING)• Consider the need for a toxicology screening. 
• Viral hepatitis serology^c• Obtain INR and recheck with each liver chemistry assessment until the transaminases values show downward trend• Obtain blood sample for PK analysis at predose and at 0.5, 1, 1.5, 2, 4, 8, 12, 24, 36, 48, 72, and 96 hours after minzasolmin administration^d• CPK and LDH• Fractionate bilirubin, if total bilirubin \geq 2xULN

Table 10-3: Phase 1 liver chemistry stopping criteria and follow up assessments table


MONITORING:
 
If ALT \geq3xULN AND bilirubin \geq2xULN or INR >1.5:
 
 Repeat liver function tests (include ALT, AST, ALP, bilirubin) and perform liver function follow-up assessments within 24 hours. Monitor participant twice weekly until liver function test abnormalities resolve, stabilize, or return to baseline. A specialist or hepatology consultation is recommended. 
If ALT \geq3xULN AND bilirubin $<$2xULN and INR \leq1.5:
 
 Repeat liver function tests (include ALT, AST, ALP, bilirubin) and perform liver function follow-up assessments within 24 to 72 hours. Monitor participants weekly until liver function abnormalities resolve, stabilize, or return to baseline. 	
 Complete blood count with differential to assess eosinophilia Record the appearance or worsening of clinical symptoms of liver injury, or hypersensitivity Record use of concomitant medications (including acetaminophen, herbal remedies, and other over-the-counter medications) Record alcohol use 
If ALT \geq3xULN AND bilirubin \geq2xULN or INR >1.5:
 
 Anti-nuclear antibody, anti-smooth muscle antibody, Type 1 anti-liver kidney microsomal antibodies, and quantitative total IgG or gamma globulins Serum acetaminophen adduct assay, when available, to assess potential acetaminophen contribution to liver injury in participants with definite or likely acetaminophen use in the preceding week. NOTE: Not required in China. Liver imaging (ultrasound, magnetic resonance, or computerized tomography) and/or liver biopsy to evaluate liver disease
---	--

AE=adverse event; ALP=alkaline phosphatase; ALT=alanine aminotransferase; AST=aspartate aminotransferase; CPK=serum creatine phosphokinase; HBsAg=hepatitis B surface antigen; HBcAb=hepatitis B core antibody; HPLC=high performance liquid chromatography; IgG=immunoglobulin G; IgM=immunoglobulin M; INR=international normalized ratio; LDH=lactate dehydrogenase; PK=pharmacokinetic(s); RNA=ribonucleic acid; SAE=serious adverse event; ULN=upper limit of normal

^a Serum bilirubin fractionation should be performed if testing is available. If serum bilirubin fractionation is not immediately available, discontinue study intervention if ALT \geq 3xULN and bilirubin \geq 2xULN. Additionally, if serum bilirubin fractionation testing is unavailable, **record the absence/presence of detectable urinary bilirubin on dipstick** which is indicative of direct bilirubin elevations suggesting liver injury.

^b All events of ALT \geq 3xULN and bilirubin \geq 2xULN ($>35\%$ direct bilirubin) or ALT \geq 3xULN and INR >1.5 may indicate severe liver injury (**possible 'Hy's Law'**) and **must be reported as an SAE (excluding studies of hepatic impairment or cirrhosis)**. The INR measurement is not required and the stated threshold value will not apply to participants receiving anticoagulants.

^c Includes: Hepatitis A IgM antibody; HBsAg and HBcAb; hepatitis C RNA; cytomegalovirus IgM antibody; Epstein-Barr viral capsid antigen IgM antibody (or if unavailable, heterophile antibody or monospot testing); and hepatitis E IgM antibody.

^d PK sample may not be required for participants known to be receiving placebo or noncomparator interventions. Record the date/time of the PK blood sample draw and the date/time of the final dose of study intervention before the PK blood sample draw. If the date or time of the final dose is unclear, provide the participant's best approximation. If the date/time of the final cannot be approximated OR a PK sample cannot be collected in the

Table 10–3: Phase 1 liver chemistry stopping criteria and follow up assessments table

time period indicated above, do not obtain a PK sample. Instructions for sample handling and shipping are in the Study Reference Manual.

This document cannot be used to support any marketing application and any extensions or variations thereof.
PUBLIC COPY

10.7

Appendix 7: Device adverse events (AEs), adverse device effects (ADEs), serious adverse events (SAEs), and device deficiencies: Definition and procedures for recording, evaluating, follow-up, and reporting

Not applicable.

This document cannot be used to support any marketing authorization application and any extensions or variations thereof.

PUBLIC COPY

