8.4.6 Adverse events of special interest

An adverse event of special interest (AESI) is any AE that a regulatory authority has mandated be reported on an expedited basis, regardless of the seriousness, expectedness, or relatedness of the AE to the administration of a UCB product/compound or associated medical device. For minzasolmin, the following events require immediate reporting (within 24 hours regardless of seriousness) to UCB:

- Possible Hy's Law (as per Section 7.1.1)
 - Potential Hy's Law, defined as $\geq 3 \times \text{ULN}$, ALT or AST with coexisting $\geq 2 \times \text{ULN}$ total bilirubin in the absence of $\geq 2 \times \text{ULN}$ ALP, with no alternative explanation for the biochemical abnormality (ie, without waiting for any additional etiologic investigations to have been concluded). Follow up information should be reported if an alternative etiology is identified during investigation and monitoring of the participant.

- Hypersensitivity reactions (such as rash, angioedema, or anaphylaxis)

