Other screening tests	
Total immunoglobulin E testUrine alcohol and cotinine testFollicle stimulating hormone and estradiol (females only)Urine drug screen (to include at minimum: amphetamines, barbiturates, cocaine, opiates, cannabinoids, and benzodiazepines, creatinine [to exclude dilution of urine samples])Serology (HIV antibody, HBsAg, HCV-Ab, and HBcAb [IgG and IgM]) 
The results of each test must be entered into ClinBase.

ALP=alkaline phosphatase; ALT=alanine aminotransferase; aPTT=activated partial prothrombin time; AST=aspartate aminotransferase; HBcAb=hepatitis B core antibody; HBsAg=hepatitis B surface antigen; HCV-Ab=hepatitis C virus antibody; HIV=human immunodeficiency virus; IgG=immunoglobulin G; IgM=immunoglobulin M; INR=international normalized ratio; PT=prothrombin time; RBC=red blood cell; ULN=upper limit of normal; WBC=white blood cell

^aBlood hematology and chemistry laboratory tests will be obtained in the fasting state following an overnight fast of at least 10 hours.

^bDetails of liver chemistry stopping criteria and required actions and follow up are given in Section 7.1.1 and Section 10.6. All events of ALT [or AST] $\geq 3 \times$ ULN and bilirubin $\geq 2 \times$ ULN ($>35\%$ direct bilirubin) or ALT [or AST] $\geq 3 \times$ ULN and INR >1.5 , (if INR measured) which may indicate severe liver injury (possible Hy's Law), must be reported to UCB in an expedited manner (excluding studies of hepatic impairment or cirrhosis).

^cThe following parameters are part of hepatic function testing: ALP, ALT, AST, and bilirubin.

^dIf ALP is elevated, consider fractionating.

^eEstimated glomerular filtration rate, based on the Chronic Kidney Disease Epidemiology Collaboration 2021 equation, only at screening.

Investigators must document their review of each laboratory safety report.

10.3 Appendix 3: Adverse events – Definitions and procedures for recording, evaluating, follow up, and reporting

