6.1.7 AEs of Special Interest

AE of special interest are:

- Possible Hy's Law: Potential Hy's Law is defined as $\geq 3 \times \text{ULN}$, ALT or AST with coexisting $\geq 2 \times \text{ULN}$ total bilirubin in the absence of $\geq 2 \times \text{ULN}$ ALP, with no alternative explanation for the biochemical abnormality (ie, without waiting for any additional etiologic investigations to have been concluded).
- Hypersensitivity reactions (such as rash, angioedema, or anaphylaxis).

A listing will be produced of Potential Hy's Law for the SS by formulation and feeding condition.

A listing will be produced for Hypersensitivity reactions for the SS by formulation and feeding condition group using the following search strategy: Standardized MedDRA Queries (SMQ)='Hypersensitivity' (Broad) AND SMQ=Anaphylactic reaction (Broad).

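### Possible Hy's Law is defined on ALT or AST, but the combined conditions in Table 10-3 that trigger SAE reporting, close monitoring and work-up name ALT alone

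*Protocol*

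**What the plan says.** Three places set the definition, and all include AST.

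- Protocol Section 8.4.6 lists potential Hy's Law as an event of special interest, with the transaminase part worded "ALT or AST with coexisting" raised total bilirubin. It requires reporting to the sponsor within 24 hours.
- Protocol Section 10.2, Table 10-1 footnote b requires expedited reporting. Its rule begins "All events of ALT [or AST" and repeats the AST bracket in its INR limb. The same footnote sends the reader to Sections 7.1.1 and 10.6 for the stopping criteria, required actions and follow-up.
- SAP Section 6.1.7 ("Possible Hy's Law: Potential Hy's Law is defined as") repeats the Section 8.4.6 thresholds, including AST.

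The actions are in Protocol Section 10.6, Table 10-3, whose only row is for absolute ALT.

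- The row's SAE rule rests on ALT with bilirubin or INR. The matching action is to "complete an SAE data collection tool if the event also met the criteria for an SAE".
- The first monitoring tier, headed by ALT with bilirubin or INR, asks for a repeat within 24 hours, a recommended specialist consultation, and: "Monitor participant twice weekly until liver function test abnormalities resolve, stabilize, or return to baseline".
- A follow-up heading with the same ALT condition covers autoimmune serology, an acetaminophen adduct assay and "Liver imaging (ultrasound, magnetic resonance, or computerized tomography) and/or liver biopsy to evaluate liver disease".
- Footnote a reads "If serum bilirubin fractionation is not immediately available, discontinue study intervention if ALT" and bilirubin reach their thresholds.
- Footnote b says that ALT with bilirubin, or ALT with INR, may be possible Hy's Law and "must be reported as an SAE (excluding studies of hepatic impairment or cirrhosis".

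In Table 10-3, AST appears only as a test to repeat and in the abbreviation list.

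**The concern.** The definition and the action table cover different participants. Table 10-1 footnote b and Table 10-3 footnote b show this most clearly. They use the same thresholds (transaminase 3×ULN, bilirubin 2×ULN with more than 35% direct, INR above 1.5) and the same label, but one includes AST and the other does not. Nothing in the protocol explains the omission.

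A site that identifies an AST-driven case and follows the cross-reference to Section 10.6 finds no combined condition that fits. For that participant the table does not call for SAE reporting, the 24-hour repeat, twice-weekly monitoring, the hepatology recommendation, or the autoimmune and imaging work-up. AST is measured on Day 5 and Day 10, 24 hours before the next dose (Schedule of Activities, footnote e), so such a case could appear between doses. What is at stake is participant safety and consistent seriousness coding. No PK analysis is affected.

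**Working it through.** No formula applies. The check compares the conditions and then runs one case through them.

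**Step 1: which transaminase each rule names**

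| Rule | Location | Names AST? |
|---|---|---|
| Potential Hy's Law | Protocol 8.4.6 | Yes |
| Footnote b, bilirubin limb | Protocol Table 10-1 | Yes |
| Footnote b, INR limb | Protocol Table 10-1 | Yes |
| Potential Hy's Law | SAP 6.1.7 | Yes |
| SAE rule | Table 10-3 | No |
| First monitoring tier | Table 10-3 | No |
| Heading for autoimmune tests and imaging | Table 10-3 | No |
| Footnote a | Table 10-3 | No |
| Footnote b, bilirubin limb | Table 10-3 | No |
| Footnote b, INR limb | Table 10-3 | No |

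Definitions naming AST: 1 + 2 + 1 = 4 of 4. Action conditions naming AST: 0 of 1 + 1 + 1 + 1 + 2 = 6.

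Three other ALT-only conditions are left out because they contradict nothing elsewhere: the ALT ≥3×ULN trigger row, the second monitoring tier (bilirubin and INR not raised), and the Section 10.6 requirement for an agreed monitoring plan when ALT exceeds 5×ULN.

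**Step 2: a worked case (hypothetical)**

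Take total bilirubin 2.5×ULN with more than 35% direct, normal ALP and INR, and no other explanation.

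| Condition in Table 10-3 | AST 4×, ALT 2× | ALT 4×, AST 2× |
|---|---|---|
| SAE rule | Not met | Met |
| First monitoring tier | Not met | Met |
| Heading for autoimmune tests and imaging | Not met | Met |
| Footnote a | Not met | Not met (fractionation was available) |
| Footnote b, bilirubin limb | Not met | Met |
| Footnote b, INR limb | Not met | Not met (INR normal) |
| Total | 0 of 6 | 4 of 6 |

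Both versions are possible Hy's Law under Section 8.4.6, Table 10-1 footnote b and SAP 6.1.7.

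**Step 3: what still applies to the AST case**

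- Reporting within 24 hours as an event of special interest (8.4.6) and expedited reporting (Table 10-1 footnote b).
- The general duty to assess potential drug-induced liver injury (10.6).
- Repeat of clinically significant laboratory values (8.3.4) and follow-up of adverse events (8.4.3).
- Extra evaluations on medical grounds or at the sponsor's request (10.3.3).
- Classification as an SAE by investigator judgement (10.3.2).

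None of these sets the Table 10-3 schedule, and SAE classification by judgement is weaker than a mandatory rule.

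**Step 4: how often it might matter**

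Section 2.3 reports 8 cases of AST and/or ALT above 3×ULN among 496 participants in the ongoing Phase 2 study: 8/496 = 1.6%. None of the 8 had raised bilirubin or INR, and most arose 2 to 3 months after the first dose. The AST-driven share is not given. Here there are three single doses ending on Day 11, and AST above 1.0×ULN excludes a participant at entry (exclusion criterion 16a).

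**The case against.** The strongest objection concerns Figure 7-1. Section 8.4.6 ties possible Hy's Law to Section 7.1.1, which rests on that figure. The figure is not shown, but its abbreviation list includes AST, so the stopping algorithm may well use AST and lead sites into Appendix 6. That is a fair possibility, and no claim is made here about whether dosing stops on AST. It does not change the wording of Table 10-3, which is what a site reads on arriving there.

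A second objection is that little is lost in practice. Events of special interest and SAEs share the same 24-hour limit, Section 8.4.6 itself expects investigation and monitoring of such a participant, the consultation is only recommended, and the appendix is titled as suggested actions. This limits the consequence and is accepted. What remains is the mandatory SAE classification, the fixed repeat and monitoring intervals, and the specified work-up.

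A third is that the count depends on grouping. Adding the second monitoring tier gives seven conditions; adding it and treating footnote b as one gives six again. The totals of 0 and 4 of 6 therefore belong to the grouping shown. That no condition names AST holds under any grouping.

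Finally, the event is very unlikely in 18 healthy participants. That is accepted and sets the severity.

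**Conclusion.** The point holds as a minor internal inconsistency. All four definitional conditions include AST, and none of the six matching conditions in Table 10-3 does. An AST-driven possible Hy's Law case thus falls outside the table's SAE rule, 24-hour repeat, twice-weekly monitoring, hepatology recommendation and extended work-up, although it remains reportable and subject to general follow-up.

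The conclusion rests on the text of Table 10-3 and its footnotes and does not depend on Figure 7-1. The worked case illustrates the gap; the documents report no such case. The frequency here cannot be estimated beyond saying that it should be low.

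**What to change.** In Table 10-3, write *ALT or AST* in the SAE rule, the first monitoring tier, the heading for autoimmune tests and imaging, footnote a, and both limbs of footnote b. State that the table's actions apply to any case meeting one of these conditions, because the row itself is entered on ALT alone. Check that Figure 7-1 agrees. Whether an isolated AST rise should also be a trigger is the sponsor's choice and is not proposed here.

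The cost is wording in six conditions. AST is already in every hepatic function test (Table 10-1 footnote c), so no routine test is added. If Figure 7-1 does not already stop dosing on AST, the change would add a permanent stop for AST ≥3×ULN with bilirubin ≥2×ULN or INR above 1.5. Such a dropout would not be replaced (Protocol 9.4). For the primary comparison at a geometric mean ratio of 0.95, the protocol gives 96% power for 18 completers and 92% for 15. One loss leaves 18 − 1 = 17, with power between those two values.
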